### **Study Population**

Patients to be enrolled will be childhood stroke survivors aged 5-19 yrs. 'Childhood' stroke is defined by the American Heart Association as stroke occurring from 29 days of life to 18 years of life.

– **Inclusion Criteria:**

- 1) Childhood stroke survivor - either arterial ischemic stroke or intracerebral hemorrhage.
- 2) Stroke must be childhood onset, defined as occurring day 29 of life to 18 years of age (per the American Heart Association's definition of childhood stroke)
- 3) 3 months or greater from stroke onset
- 4) Arm impairment, defined as pediatric stroke outcome measure of 1 or greater of affected arm.
- 5) Affected arm Fugl-Meyer score of 60 or lower.
- 6) Able to participate in occupational therapy sessions.

– **Exclusion Criteria:**

- 1) Uncontrolled epilepsy, defined as seizure within the past 6 months.
- 2) Craniectomy without replacement of bone flap. Patients who underwent craniectomy will need the bone flap reattached prior to participation.
- 3) Presence of cranial metal implants or implant device that could be affected by tDCS: cochlear implant, implanted brain stimulator, or programmable ventriculoperitoneal shunt.

Patients will be identified in the UTHealth Pediatric Stroke clinic by the PI, [name]. Flyers for the study will also be available on the UTHealth website. The flyer is included in the study documents.

### **Study Procedures**

- There will be 3 assessment visits and 5 therapy visits.
- Baseline assessment visit: This visit will take approximately 2 hours. A study physician will fill out the 'medical history' form and complete the Pediatric Stroke Outcome Measure
  - The Pediatric Stroke Outcome Measure is a standardized neurologic exam used for childhood stroke survivors.

- The therapist will complete 4 tests:
  - 1) Fugl-Meyer test, a 30 minute therapy evaluation tool to assess arm function
  - 2) The Canadian Occupational Performance Measure, a structured interview to assess activities of daily living
  - 3) The Box and Blocks test – a two minute test of hand dexterity in which the subject moves blocks from one area to another while remaining seated.
  - 4) Melbourne Assessment of the Upper Extremity, a 30 minute unilateral assessment of the affected arm.
- 5 occupational therapy sessions. These will take approximately 2 hours each.
- The 2 follow up assessments are done at 1 week and 3 months post intervention. Each which will take 1-2 hours. A study physician will perform the Pediatric Stroke Outcome Measure, and the study therapist will perform the Fugl-Meyer test, the Canadian Occupational Performance Measure, Melbourne Assessment of the Upper Extremity and the Box and Blocks test.

### **Data and Safety Monitoring**

- No major adverse events are expected. We will monitor for hypotension, tachycardia, and mild side effects like headache. We expect about 40% of patients will endorse the expected mild side effects: headache, numbness or tingling. We expect no patients will develop hypotension or tachycardia.
- If any patient does have a major adverse event, the intervention will be stopped, the event will be logged on the case report form and the patient will be given all usual emergency medical care. The event will be sent to the Data Safety Monitoring Board who will independently review the event and decide whether the event was caused by the intervention. If it is, the study will be discontinued and the protocol revised.
- There is a two person Data Safety Monitoring Board. Case Report Forms for all participants will be sent to the DSMB electronically after completion of the 1st follow up assessment visit (1 week post intervention) for review. The DSMB will need to approve that the study can continue prior to beginning the intervention for the next patient.

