### Outcome Measures:

- Tolerability Primary outcome measure:
  - Percent of patients who complete the study, as defined by patients who complete the 1-week post therapy assessment visit. Patients who voluntarily withdraw for any

- reason or who stop due to an adverse event will be defined as not completing the study.
- Tolerability Secondary outcome measures
  - Percent of patients that endorse mild side effects as documented on the stimulation monitoring sheet. The stimulation monitoring sheet is filled out during each stimulation session pre and post stimulation.
  - Percent of patients with hypotension or hypertension on blood pressure monitoring post stimulation and post therapy session. Time points for data collection will be pre-stimulation, post-stimulation, and post-therapy session.
  - Percent of patients with worsening of the Peg-board test (decreased score by 5 or greater) on the Peg-Board Test post stimulation and at the end of therapy session compared to baseline score. Time point will be the end of each therapy session.
- Improvement in Arm Function Primary outcome measure
  - Increase of 5 points or more on the Fugl-Meyer score of Upper extremity function at the 1 week post therapy assessment.
- Improvement in Arm Function Secondary Outcome Measure
  - Increase of 5 points or more on the Fugl-Meyer score of upper extremity function at the 3 month post therapy assessment.

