### **Study Design**

- This study is an unblinded interventional trial.
- Subjects will be childhood stroke survivors with chronic arm impairment, defined below in the inclusion and exclusion criteria. 5 patients total will be enrolled.

The Primary Objective is to assess tolerability of tDCS. Tolerability will be evaluated by

- The percent of patients who are able to complete the study
  - If any patients drop out due to tDCS related side effects, this would be considered poorly tolerated.
- The percent of patients that endorse mild side effects as documented on the 'Stimulation Monitoring Sheet' (included separately)
  - We expect 40% of patients to endorse mild side effects per session that will be non-treatment limiting.
- Monitoring of Peg-Board test results pre stimulation, post stimulation, and at the end therapy session to ensure no decrease (worsening) in score poststimulation.
- Monitoring of Vital Signs (pulse and blood pressure) pre stimulation, post stimulation, and at the end of the therapy session.
- Study description and sample timeline:
  - On enrollment, patients will have a study visit where they will have a Pediatric Stroke Outcome Measure completed by the PI as well as a medical history with the enrollment form. The study therapist will then complete the following assessments – Fugl-MeyerScore, Canadian Occupational Performance Measure, Box and Blocks test, Melbourne.
  - The patient will then come for 5 sequential days of 2 hour long occupational therapy sessions augmented by tDCS for the first 20 minutes of the session. At arrival, the "stimulation safety sheet" will be completed by the occupational therapist (form attached). The saline soaked electrodes will be placed on the study subjects head and connected to the

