Soterix 1x1 LTE enabled tDCS device. Prior to beginning stimulation, the "Investigator Screening Form" checklist will be completed for each patient during each stimulation. Current output through the device will be sham stimulation on day 1, followed by steady increases to a maximum of 1mA in patients aged 5-12 years old, and 1.5mA in patients aged 13-19 years old, per the study design flow sheet at the end of this protocol. The child and parents will be blinded to the sham stimulation. The investigators will not be, since all patients receive the same age based current protocol. Consequently, investigators will be aware it is sham stimulation on day 1. We have chosen to have sham stimulation on the first day to acquire baseline data for tolerability and reported side effects without current being passed through the electrodes, which we will report with descriptive statistics. Blood pressure, pulse rate, and peg-board scores will be recorded as indicated on the stimulation safety sheet during each session.

- A repeat assessment will be done by the occupational therapist one week post therapy completion.
- There will be a repeat assessment visit 3 months post intervention.

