#### **ATTACHMENTS**

1. Schematic of Study Design
2. Study Schedule
3. Consent Documents
  - Parental, English and spanish
  - Patient, English and spanish
  - 7-17 year old Assent Forms, English and spanish
4. Case Report Form
  - Medical History
  - PSOM
  - Pre-intervention OT assessment forms
    - Fugl Meyer- Upper Extremity
    - Box and Blocks CRF
    - COPM to be performed through web based application – <https://app.thecopm.ca>
    - Melbourne Assessment of the Upper Extremity CRF
  - Day of tDCS screening sheet
  - Day of tDCS safety sheet
  - Post-intervention OT assessments
    - Fugl Meyer- Upper Extremity
    - Box and Blocks CRF
    - COPM to be performed through web based application – <https://app.thecopm.ca>
    - Melbourne Assessment of the Upper Extremity CRF

- 3 month post-intervention OT assessments
  - Fugl Meyer- Upper Extremity
  - Box and Blocks CRF
  - COPM to be performed through web based application – <https://app.thecopm.ca>
  - Melbourne Assessment of the Upper Extremity CRF
- 5. Linking Log
- 6. Flyer

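### Study completion, the primary tolerability outcome, requires no active sessions or delivered current, so a child whose stimulation was held, lowered or missed because of a harm can still count as a completer

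*Combined protocol and SAP*

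**What the plan says.** Outcome Measures gives the primary tolerability outcome as "Percent of patients who complete the study, as defined by patients who complete the 1-week post therapy assessment visit". The exception covers patients who withdraw voluntarily and those "who stop due to an adverse event will be defined as not completing the study". Study Design adds an interpretation: "If any patients drop out due to tDCS related side effects, this would be considered poorly tolerated".

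Study Design describes five consecutive daily sessions with stimulation in the first 20 minutes. Day 1 is sham; the current then rises to a maximum of 1 mA at ages 5-12 or 1.5 mA at ages 13-19. Investigators know that day 1 is sham, "since all patients receive the same age based current protocol". The day-by-day steps are on a flow sheet that is not in the supplied text.

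Pulse, blood pressure and Peg-Board are measured before stimulation, after it, and at the end of the session. An Investigator Screening Form is filled in before each stimulation. A stimulation safety sheet "will be completed by the occupational therapist (form attached"), and Attachments lists a "Day of tDCS safety sheet" within the Case Report Form.

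The secondary tolerability outcomes are the percentages of patients with mild side effects, with abnormal blood pressure, and with a Peg-Board fall of 5 or more. Data and Safety Monitoring states "If any patient does have a major adverse event, the intervention will be stopped". It also requires the DSMB to review each child's forms after the one-week visit and approve continuation before the next child starts.

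**The concern.** The primary objective is the tolerability of tDCS, but the primary outcome measures attendance at a follow-up visit. The two agree when every child receives every active session as scheduled. They part when a session is held, given at a lower current or missed because of a harm, and the child then continues and returns at one week. Under the definition that child is a completer.

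The trial could then report that all 5 children completed although fewer had tolerated the scheduled current. A later study taking its current from this trial would want the second figure, and no listed outcome supplies it. The secondary outcomes show that a harm occurred, but not whether the child's stimulation changed as a result.

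A related case is unclear. If stimulation is stopped for good because of an adverse event and the child is still seen at one week, as good follow-up would intend, the child satisfies the attendance definition and also the exception.

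**Working it through.** The plan states no figure to reproduce: the sample size of 5 comes without a power calculation, and Statistics promises only descriptive results. The check applies the definition case by case and then counts.

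**Inputs**
- Children: 5 (Study Design; Statistics).
- Sessions per child: 5, the first sham (Study Design).
- Completion rule and exception: Outcome Measures.
- Assumption: active current on each of days 2-5. The flow sheet that would confirm this was not supplied.

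**Step 1. Apply the definition**

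| What happens to the child | Status as written |
|---|---|
| Receives all sessions as scheduled, attends at 1 week | Completer |
| Withdraws, or stops for an adverse event, and does not attend | Non-completer |
| An active session is held, lowered or missed because of a harm; child continues and attends | Completer |
| Stimulation stopped for good for an adverse event; child attends | Fits both sentences; unclear |

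**Step 2. Size of the gap**

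Let all 5 attend, and let k of them have at least one active session held, lowered or missed because of a harm.
- Primary outcome as written: 5/5 = 100% for every k.
- Completion at the scheduled current: (5 − k)/5.
- For k = 0, 1, 2, 3, 4, 5 this is 100, 80, 60, 40, 20, 0%.
- Gap: k × 20 percentage points.

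The documents give no rate for such events. As an illustration, suppose each child independently has probability p of one. The chance of at least one among 5 is 1 − (1 − p)^5, which is 22.6, 41.0, 67.2 or 83.2% for assumed p of 5, 10, 20 or 30%.

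Exact 95% intervals are 47.8-100% for 5/5, 28.4-99.5% for 4/5 and 14.7-94.7% for 3/5. They overlap widely. The issue is therefore what the reported number counts, not statistical precision.

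**Step 3. Can a reader recover the missing figure?**

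Suppose the report shows 5 of 5 completing and 1 of 5 with Peg-Board worsening. That fits a child who went on at full current and equally a child whose next session was lowered. The listed outcomes do not separate the two. Pulse is monitored but is not among the outcomes in Outcome Measures, so a session held for tachycardia need not appear in any of them.

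**Step 4. Number of sessions to account for**

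4 active days × 5 children = 20 active sessions at most.

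**The case against.** The case for leaving the text alone is substantial.

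- Completion is only one of four components by which Objectives and Study Design evaluate tolerability. Mild side effects, Peg-Board and vital signs are the others, so in a five-patient report a 5/5 would stand beside any blood pressure or Peg-Board harm.
- Stopping for an adverse event of any grade is already non-completion.
- No part of the text describes a held, lowered or missed session, so the scenario is hypothetical.

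All of this stands, and it is why the point is minor. It does not close the gap: the harms are visible, but the current received after them is not. The scenario also needs no formal hold rule, because a missed day is enough.

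A reader might go further and infer that current rises on the age schedule whatever the monitoring shows, or that nothing short of a major event or drop-out has any consequence. The documents do not support either reading. The remark that all children share one age-based schedule explains why investigators are unblinded; it does not forbid adjustment. A checklist and fresh readings precede each stimulation, and that checklist, the safety sheet and the flow sheet were not supplied. The most that can be said is that the supplied text states no hold or lower rule. Lesser findings can also matter through the any-grade stopping clause and the DSMB's approval before the next child, although that review comes too late to alter the same child's sessions.

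Mild side effects are outside this point: "We expect 40% of patients to endorse mild side effects per session that will be non-treatment limiting".

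**Conclusion.** The point holds for the definition of completion, and it holds whatever the unsupplied forms contain. As written, the primary result can read 100% while completion at the scheduled current is anywhere from 100% down to 0%, at 20 percentage points per affected child. The two figures differ only if some child has an active session held, lowered or missed because of a harm and still attends at one week. How likely that is cannot be judged from the documents.

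The reading assumes that stopping for an adverse event means ending participation or stimulation, not pausing a single session. The status of a child permanently stopped but seen at one week is ambiguous and should be settled in advance.

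This is a cheap improvement of minor severity. It is not evidence that children are unprotected during the study.

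**What to change.** In Outcome Measures, after the definition of completion, add:

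*Completion will also be reported as the number of the 5 patients who received all active sessions at the age-scheduled current. Every held, lowered or omitted session will be listed with its reason. A patient whose stimulation is permanently stopped for an adverse event is a non-completer, even if the 1-week visit is attended.*

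If the day-of-tDCS forms contain hold criteria, cite them in Data and Safety Monitoring. I propose no new numerical threshold or extra review step, since either could duplicate those forms.

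The cost is a short listing covering at most 20 active sessions (assuming active current on days 2-5). If the daily sheets do not already record the current delivered, they need one added line. The added completion figure may look less favourable than the present one. Sample size, visits and DSMB duties do not change. The listing would also show directly whether mild side effects were non-limiting, as the plan expects.

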### **Statistics**

- As this is a 5 patient tolerability study, only descriptive statistics will be used.
- 5 patients total will be enrolled, and results will be reported with descriptive statistics.
- The trial will be terminated if there is a major safety event deemed to be due to the intervention by the DSMB.
- All subjects will be included in the descriptive analysis.

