### **Data handling and record keeping**

- Source documents will be kept in a double-locked cabinet in the Center for Treatment of Pediatric Neurodegenerative Disease, [name].
- CRF data will be entered into a password protected redcaps database after completion by study staff. A linking log with patient identifiers (name, DOB) will be kept in a folder in the redcaps database.
- Only the PI, Co-PI, DSMB, research nurse, OT, and research coordinator will have access to patient information via the redcaps database.
- Human subjects will be not be identifiable through case report forms.
- Special Note: The Canadian Occupational Performance Measure is completed through a web-based application available at <https://app.thecopm.ca>. Once completed, the COPM printout will be downloaded and stored in the redcaps database.

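### Could a child who leaves before the 1-week visit because of mild side effects go unreviewed by the DSMB before the next child starts?

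*Combined protocol and SAP*

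**What the plan says.** All of this is in the combined protocol and SAP.

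- **Data and Safety Monitoring, routine route.** "Case Report Forms for all participants will be sent to the DSMB electronically after completion of the" first follow-up visit, which is set one week after the intervention.
- **Data and Safety Monitoring, approval step.** "The DSMB will need to approve that the study can continue prior to beginning the intervention for the next patient".
- **Data and Safety Monitoring, event route.** A major adverse event is sent to the DSMB, which judges whether the intervention caused it. The Statistics section gives the consequence: "The trial will be terminated if there is a major safety event deemed to be due to the intervention by the DSMB".
- **Outcome Measures.** The primary tolerability outcome is "Percent of patients who complete the study, as defined by patients who complete the 1-week post therapy assessment visit". Children who withdraw voluntarily for any "reason or who stop due to an adverse event will be defined as not completing the study".
- **Study Design.** "If any patients drop out due to tDCS related side effects, this would be considered poorly tolerated".
- **Data handling and record keeping.** "Only the PI, Co-PI, DSMB, research nurse, OT, and research coordinator will have access to patient information via the redcaps database". Case report form data are entered into that database.
- **Quality control and assurance.** This section only refers back to the DSMB monitoring already described.

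**The concern.** The same visit does two jobs. It defines a completer, and it times the routine sending of forms to the DSMB. A child who drops out before it because of headache or tingling is a non-completer and also never produces the event that times the sending. Nor does the major-event route apply.

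Read literally, this leaves two unattractive outcomes. Either the next child waits for a visit that will not take place, or the DSMB gives its approval without the withdrawn child's forms. The second would matter. Tolerability is the primary objective, child-by-child DSMB review is a main safeguard, and a drop-out caused by tDCS side effects is the event that the Study Design section treats as decisive for tolerability. It would be odd if that event were the one with no stated path to the board.

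**Working it through.** No figure in the plan can be reproduced here. The sample of 5 is stated without a derivation, the analysis is descriptive, and no drop-out rate is given. The check is therefore to trace each kind of child through the text.

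1. **The child attends the 1-week visit.** The forms are sent, the DSMB reviews them, and approval is sought. This includes a child who stops stimulation early but still attends. There is no gap.
2. **The child has a major adverse event.** The event goes to the DSMB by its own route, whatever happens to the visit. There is no gap.
3. **The child leaves before the 1-week visit because of non-major side effects.** No sending time is stated. This is the only case in question.

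For the third case, two points must be kept apart: whether the forms are owed to the DSMB, and when.

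- *Whether.* The sentence covers all participants. A child who withdraws is still a participant, and the Statistics section likewise includes all subjects in the descriptive analysis. The forms are owed.
- *When.* The visit sets the usual date, and for this child no date is written. That is the whole of the gap.

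The approval step then decides what follows. It applies before every next child and has no exception for withdrawals.

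- *If the forms are late,* the next child waits. Nobody is exposed, and sending the forms ends the wait.
- *If the DSMB is asked to approve,* that request is itself a review point after the withdrawn child. The board can ask for the forms or read the data in the database. Approving without them would go against the duty to send every participant's forms; the plan does not prescribe it.

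**How often the case might arise.** This needs assumptions. Let p be the chance that a child stops before the visit for non-major tDCS side effects, and a the share of such children who still attend. Four of the five children are followed by another child, so the chance of at least one case that bears on a later child is 1 − (1 − p(1 − a))^4.

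| Assumed p | a = 0 | a = 0.5 |
|---|---|---|
| 5% | 1 − 0.95^4 = 0.185 | 1 − 0.975^4 = 0.096 |
| 10% | 1 − 0.90^4 = 0.344 | 1 − 0.95^4 = 0.185 |
| 20% | 1 − 0.80^4 = 0.590 | 1 − 0.90^4 = 0.344 |

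These are chances that the situation occurs, not that the DSMB misses it. Because approval is mandatory in every row, the table does not measure harm and carries no weight in the conclusion.

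**The case for a change.** The strongest case for a change is that intent and database access are not a procedure. Naming all participants shows what the authors wanted, but the timing still hangs on a visit that the withdrawn child does not make. Access to the database carries no duty to look at it. Nothing lists what the DSMB must have seen before it approves. In so small a trial one such child is 1/5 = 20% of the sample, and a sentence would close the gap at the cost of one extra transmission of forms. Even for a child who stops early but attends, the visit date is loose: the Study Design section has "A repeat assessment will be done by the occupational therapist one week post therapy completion", while the monitoring section counts from the intervention, and neither covers therapy that ends early.

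The textual point stands: no sending time is stated for this child. The consequence does not. For the next child to start without review of the withdrawn child, staff would have to leave out forms the plan says are sent, and the DSMB would have to approve without asking about the child just treated.

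The statement about poor tolerability concerns how the result is judged, whereas the termination rule concerns major events attributed to the intervention. The two do not conflict, so they need no reconciling. The day-count point is also minor. Therapy and stimulation belong to the same block of 5 daily sessions, so the ambiguity is a few days and does not affect whether forms reach the board.

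**Conclusion.** No change is called for. The plan leaves out a sending date for one narrow group: children who leave before the 1-week visit for non-major side effects and do not attend it. Staff would fill this gap sensibly by sending the forms, with the reason for stopping, when they ask for approval to treat the next child. Followed as written, the plan still puts a DSMB decision between each child and the next, and the withdrawn child still counts as a non-completer in the primary outcome.

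In size, this is a missing administrative detail. It alters no estimate, denominator, stopping rule or sample size. The conclusion rests on two readings: that the duty to send forms covers withdrawn children, and that the approval step has no exceptions. The wording of the Data and Safety Monitoring section supports both. It does not depend on any assumed drop-out rate.
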